11.0 Provisions to Monitor the Data to Ensure the Safety of Subjects

Safety will be monitored throughout the study based on the monitoring of adverse events, performing nasal exams, measuring vital signs (i.e. blood pressure, pulse) and weight, and through the collection of concomitant medication information.

The period of observation for collection of non-serious adverse events extends from the time the subject gives informed consent until the completion of the End-of-Study visit or Early Termination Visit. Serious adverse events (SAE) will be reported to the MUSC IRB and to the sponsor from the time of informed consent through 30 days after the last use of the SinuSonic. Adverse event data listings will be reviewed by Principal Investigator and the research team at regular intervals throughout the study.

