6.0 Setting

Research will be conducted at the Medical University of South Carolina. Potential participant screening for all subjects across all aims, as well as baseline evaluations, will occur in the outpatient ENT clinics. For AIM 2, the 6-week post treatment assessment will take place in the outpatient ENT clinics. For AIM 3, follow-up measures will be collected remotely using REDCap at 2 and 4 weeks.

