9.1 Schedule of Events

Aim 1: NO in N=10 controls	Screening and baseline assessment
Day	0
Informed consent	X
Inclusion/exclusion criteria	X
Medical history	X
Rhinology, otoscopy	X
Vital signs	X
Exhaled nasalNO at 30 seconds and 5 min	X

Aim 2: ETD efficacy in N=30 patients	Screening and baseline assessment	Primary timepoint for outcomes
Week	0	6 + 1
Informed consent	X	
Inclusion/exclusion criteria	X	
Medical history	X	
Rhinology, otoscopy	X	X
Vital signs	X	
Distribution of Sinusonic	X	X
ETDQ-7	X	X
ETD VAS questionnaire	X	X
Tympanogram	X	X

Aim 3: Facial pain/pressure in N=30 patients	Screening and baseline assessment	Primary timepoint for outcomes	Secondary timepoint for outcomes
Week	0	2	4
Informed consent	X		
Inclusion/exclusion criteria	X		
Medical history	X		
Rhinology, otoscopy	X		

Vital signs	X		
Distribution of Sinusonic	X		
Pain/pressure VAS	X	X	X
BPI-SF	X	X	X
MPQ-SF	X	X	X

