12.0 Risks to Subjects

There is a risk of a loss of confidentiality of your personal information as a result of participation in this study.

There are risks to subjects using the SinuSonic device. Subjects may experience a degree of pain due to use of the device. This degree of pain is unknown. There may also be risk of nose bleeds or crusting around the nasal cavity.

The Rhinoscopy may activate the gag reflex. Additionally, nasal discomfort, nose bleeds, spasms, and coughing may also occur.

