19.0 DATA SAFETY MONITORING AND REPORTING

Safety data listings will be reviewed by Principal Investigator, Co-Investigators, and the research team at regular intervals throughout the study.

Safety will be monitored throughout the study based on monitoring of adverse events, performing nasal exams, measuring vital signs (ie blood pressure, pulse) and weight, and through collection of concomitant medication information.

The period of observation for collection of non-serious adverse events extends from the time the subject gives informed consent until completion of the End-of-study visit or Early Termination Visit. Serious adverse events (SAE) will be reported to the MUSC IRB and to the sponsor from the time of informed consent through 30 days after the last use of the SinuSonic. Adverse event data listings will be reviewed by the principal investigator, co-investigators, and the research team at regular intervals throughout the study.

All AEs, regardless of seriousness or relationship to SinuSonic use, spanning from the signature of the informed consent form until the end of the study as defined by the protocol for that patient, are to be reported to the Healthy Humming, LLC. All AEs which follow the MUSC IRB qualifications will also be reported to the MUSC IRB within 24 hours of site knowledge of the event.

The Investigator will take appropriate measures to follow all AEs until clinical recovery is complete and laboratory results have returned to normal, or until progression has been stabilized, or until death, in order to ensure the safety of the patients. This may imply that observations will continue beyond the last planned visit per protocol, and that additional investigations may be requested by the monitoring team up to as noticed by Healthy Humming, LLC.

In the case of occurrence of an SAE, the Investigator will immediately (within 24 hours) report the event to Healthy Humming, LLC and to the MUSC IRB, as applicable.

References

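### The safety monitoring promised across the study is not carried into the Schedule: no vital signs, weight or medication record after baseline, and no Aim 3 nasal exam or crusting question

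*Combined protocol and SAP*

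**What the plan says.** Section 11.0 opens with "Safety will be monitored throughout the study based on the monitoring of adverse events" and adds "performing nasal exams, measuring vital signs (i.e. blood pressure, pulse) and weight, and through the collection of concomitant medication information". Section 19.0 repeats this: "Safety will be monitored throughout the study based on monitoring of adverse events, performing nasal exams", followed by the same remaining items. Section 9.0 carries the same sentence, with the word for the exam missing after nasal. Non-serious events are collected "until the completion of the End-of-Study visit or Early Termination Visit". Serious events (SAEs) are reportable "from the time of informed consent through 30 days after the last use of the SinuSonic".

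In the Schedule of Events (9.1), vital signs are ticked once per aim, at day 0 or week 0. The row "Rhinology, otoscopy" is ticked at day 0 in Aim 1, at weeks 0 and 6 in Aim 2, and at week 0 only in Aim 3. Section 6.0 explains the Aim 3 pattern: "For AIM 3, follow-up measures will be collected remotely using REDCap at 2 and 4 weeks".

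Section 12.0 lists pain with device use and says "There may also be risk of nose bleeds or crusting around the nasal cavity". Safety is part of the stated objective of Aims 2 and 3 (Section 1.0), and Section 10.0 plans a safety summary at every time point.

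**The concern.** The text sections and the Schedule describe two different safety data sets. A site working from 9.1 and the appendix forms would not obtain several of the measures on which 11.0 says safety rests. For those measures, a report of no findings after baseline would mean only that nobody was asked or examined.

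The gap also reaches efficacy. Aims 2 and 3 are single-arm comparisons of each patient with his or her own baseline. Section 2.0 names nasal steroid sprays as a current treatment. The eligibility criteria exclude recent topical decongestant use but not steroid sprays, and nothing restricts starting or stopping one. If medicines are recorded only at baseline, a change during follow-up cannot be seen, let alone set apart from the device effect.

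**Working it through.** This is a check of consistency. The documents give no sample-size or safety-precision figure to reproduce, so the promised measures are set beside what is scheduled or printed on a form after baseline.

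| Measure in 9.0, 11.0, 19.0 | Aim 1 (N=10) | Aim 2 (N=30) | Aim 3 (N=30) |
|---|---|---|---|
| Nasal exam after baseline | None in 9.1; an unscheduled Day 1 form exists | Week 6, recording bleeding and crusting | None |
| Vital signs after baseline | None | None | None |
| Weight | No row; baseline form only | No row; baseline form only | No row; baseline form only |
| Medication | No row; baseline form only | No row; baseline form only | No row; baseline form only |
| Adverse events | No row | No row; week-6 form asks about device pain and bleeding | No row; weeks 2 and 4 ask about device pain and bleeding |
| Crusting | Day 1 form only | Week-6 rhinoscopy | Not asked or examined |

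No appendix form has a field for blood pressure or pulse, even at baseline.

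**Counts by the Schedule**

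- Nasal exam at a later visit: 30 of 10 + 30 + 30 = 70 planned subjects, 30/70 = 43%, all in Aim 2. Counting the Aim 1 Day 1 form, 40/70 = 57%. Aim 3: 0 of 30.
- Vital signs or weight after baseline in the home-use aims: 0 of 30 + 30 = 60.

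**SAE window**, assuming last use on the last planned day (Section 3.0) and end of window = last use + 30 days:

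- Aim 1: 0 + 30 = day 30 (day 31 if the Day 1 form reflects a real visit with device use). Last contact: day 0 or 1.
- Aim 2: 42 + 30 = day 72, or 49 + 30 = day 79 if use runs to week 7. Last scheduled contact: day 42 to 49.
- Aim 3: 28 + 30 = day 58. Last scheduled contact: day 28.

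No contact is scheduled in those 30 days in any aim. Section 9.0 mentions weekly coordinator calls, but only to assess compliance and with no end date. In Aim 2 the Schedule also ticks device distribution at week 6; if use continues after that visit, last use cannot be dated from the protocol.

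**Other places that do not line up**

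- Section 15.0 pays per visit: Aim 3 up to $150 at $50 each, 150/50 = 3 visits, while Section 6.0 makes two of the three contacts remote.
- The End-of-Study and Early Termination visits that close the non-serious event window are not named as columns in 9.1.

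**Precision is a separate matter.** With complete capture, zero events in 30 gives a one-sided 95% upper limit of 1 − 0.05^(1/30) = 9.5% and an exact two-sided limit of 1 − 0.025^(1/30) = 11.6%. For an item asked in both home-use aims, zero in 60 gives 1 − 0.05^(1/60) = 4.9% one-sided. These limits come from the sample size and would be the same under a perfect Schedule.

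**The case against.** The strongest reply is that a missing Schedule row does not mean missing data. Section 9.0 describes adverse-event listings and automated alerts from the data-capture system. Section 19.0 requires every event from consent to end of study to be reported to the company. Nothing says that the appendix forms are the full case report form. The listed device risks are pain, nose bleeds and crusting: pain and bleeding are asked in both home-use aims, crusting is examined in Aim 2, and vital signs and weight bear on none of the three. This is also an exploratory pilot, and the text promises monitoring throughout without stating a frequency.

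Much of this stands, and it rules out several stronger readings that a reader might infer:

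- *That safety is not collected in follow-up.* The reporting route, the week-6 rhinoscopy and the self-report items show otherwise.
- *That the 30 days after last use are unobserved.* The text sets a reporting window, which spontaneous reports can meet. What the documents support is that no contact is scheduled and no way of finding events is stated. The continued observation in Section 19.0 follows events already known; it does not look for new ones.
- *That the 9.5% limit measures this gap.* It measures a sample of 30.
- *That medication changes would favour the device.* Patients may stop medicines as well as start them, so the direction is unknown.

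What the reply does not answer is Aim 3 crusting, medication changes in both home-use aims, and the disagreement between the text sections and 9.1. The weekly calls could carry the missing questions, but as described they do not.

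**Conclusion.** The inconsistency is real and limited in extent. As scheduled, Aim 3 cannot report on crusting, vital signs or weight after baseline in any of its 30 patients. Aim 2 cannot report on later vital signs or weight, although it does have a nasal exam at week 6. In both aims a medication change in either direction cannot be separated from the device effect. SAEs remain reportable for 30 days after last use, with no stated means of finding them.

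This rests on reading 9.1 and the appendix forms as the working data-collection plan, and on device use ending when planned. If fuller case report forms or call scripts exist outside these documents, the gap in collection may be smaller, but the sections would still disagree. Severity: should-fix. The main local risks are mostly covered, and the remedy uses contacts already planned.

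**What to change.** The sponsor and investigator should reconcile Sections 6.0, 9.0, 9.1, 11.0, 15.0 (three paid Aim 3 visits) and 19.0 with the appendix forms, including the unscheduled Aim 1 Day 1 examination form. Which assessments are made, and when, is for them to decide. The same revision should state how SAEs are ascertained up to 30 days after last use.

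At contacts already planned (Aim 2 week 6, the Aim 3 REDCap forms at weeks 2 and 4, and the weekly calls), add two questions: any new health problem, and any new, stopped or changed medicine. Add a crusting question for Aim 3. Unless exams are scheduled there, state that Aim 3 safety after baseline is by self-report.

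In the analysis:

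- Report event rates with exact 95% confidence intervals.
- Keep all patients in the main efficacy estimate and describe medication changes alongside it.
- Present any analysis that leaves out patients whose medicines changed as a sensitivity analysis only. It conditions on a post-baseline event: dropping patients who worsened and added treatment can inflate the apparent benefit.

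The cost is a protocol revision and a few more questions per contact.

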12.0 Risks to Subjects

There is a risk of a loss of confidentiality of your personal information as a result of participation in this study.

There are risks to subjects using the SinuSonic device. Subjects may experience a degree of pain due to use of the device. This degree of pain is unknown. There may also be risk of nose bleeds or crusting around the nasal cavity.

The Rhinoscopy may activate the gag reflex. Additionally, nasal discomfort, nose bleeds, spasms, and coughing may also occur.

13.0 Potential Benefits to Subjects or Others

This study is for research purposes only. There is no direct benefit to you from your participation in the study. Information learned from the study may help other people in the future.

14.0 Sharing of Results with Subjects

Information about the subjects (including your identifiable private information) may have all of their identifiers removed and used for future research studies.

Records of the subjects' participation in this study will be held confidential except as disclosure is required by law or as described in the ICF.

15.0 Payment

For participating in this study, participants will be compensated with a \$50 Visa gift card per visit for a maximum of \$50 for the Control group, \$100 for the ETD groups and \$150 for the Facial Pain/Pressure groups.

18.0 Devices

Dispensing and storage of SinuSonic devices will be done by the study team. All SinuSonic devices will be stored on the [name] and locked in a cabinet for ambient storage. The device will be dispensed in the Outpatient Sinus Clinic. Only study participants will receive the SinuSonic for use.

19.0 DATA SAFETY MONITORING AND REPORTING

Safety data listings will be reviewed by Principal Investigator, Co-Investigators, and the research team at regular intervals throughout the study.

Safety will be monitored throughout the study based on monitoring of adverse events, performing nasal exams, measuring vital signs (ie blood pressure, pulse) and weight, and through collection of concomitant medication information.

The period of observation for collection of non-serious adverse events extends from the time the subject gives informed consent until completion of the End-of-study visit or Early Termination Visit. Serious adverse events (SAE) will be reported to the MUSC IRB and to the sponsor from the time of informed consent through 30 days after the last use of the SinuSonic. Adverse event data listings will be reviewed by the principal investigator, co-investigators, and the research team at regular intervals throughout the study.

All AEs, regardless of seriousness or relationship to SinuSonic use, spanning from the signature of the informed consent form until the end of the study as defined by the protocol for that patient, are to be reported to the Healthy Humming, LLC. All AEs which follow the MUSC IRB qualifications will also be reported to the MUSC IRB within 24 hours of site knowledge of the event.

The Investigator will take appropriate measures to follow all AEs until clinical recovery is complete and laboratory results have returned to normal, or until progression has been stabilized, or until death, in order to ensure the safety of the patients. This may imply that observations will continue beyond the last planned visit per protocol, and that additional investigations may be requested by the monitoring team up to as noticed by Healthy Humming, LLC.

In the case of occurrence of an SAE, the Investigator will immediately (within 24 hours) report the event to Healthy Humming, LLC and to the MUSC IRB, as applicable.

References


Soler ZM, Nguyen SA, Salvador C, Lackland T, Desiato VM, Storck K, Schlosser RJ. Safety and efficacy of a novel device combining acoustic vibration with oscillating expiratory pressure for the treatment of nasal congestion. *Int Forum Allergy Rhinol* (in press).

APPENDICES

AIM 1, CONTROL PATIENTS, EXHALED NO:

Baseline medical history and exam

SinuSonic Study

PI: [name]

Subject ID#: _____ Subjects Initials: _____

DEMOGRAPHIC AND CLINICAL VARIABLES (If not previously collected):

Age at enrollment (years):

--	--

Gender: Male Female

What is/was your profession (current/retired)? _____

LANGUAGE, ETHNICITY, RACE, MARITAL STATUS

Please mark one of the following categories which describes your native language:

- ☐ American English
☐ Other: please specify _____

Please mark one of the following categories which describes your ethnicity:

- ☐ Not Hispanic or Latino
☐ Hispanic or Latino

Please mark one or more of the following categories which describes your race:

- ☐ American Indian or Alaska Native
☐ Asian
☐ Black or African American
☐ Native Hawaiian or Other Pacific Islander
☐ White
☐ Other

SMOKING HISTORY

1. Do you **currently** smoke tobacco products? Yes No (If No please go to question 2)

How many tobacco products do you use in a day? _____ Singles Packs

CURRENT MEDICATION USAGE

- | | | |
|---|------------------------------|-----------------------------|
|  Nasal steroid sprays (Flonase, Nasonex, etc) |  Yes |  No |
|  Nasal antihistamine spray (Astelin, etc) |  Yes |  No |
|  Oral antihistamines (Allegra, Claritin, Benedryl, etc) |  Yes |  No |
|  Oral decongestant (Sudafed, etc) |  Yes |  No |
|  Mucolytic (Mucinex, etc) |  Yes |  No |
|  Luekotriene (Singulair, etc) |  Yes |  No |

COMORBID MEDICAL CONDITIONS: Check box and provide details if present

- ☐ Depression history: ☐ Resolved/past diagnosis ☐ Present/medicated ☐ Present/not medicated
- ☐ Anxiety history: ☐ Resolved/past diagnosis ☐ Present/medicated ☐ Present/not medicated
- ☐ Obstructive Sleep Apnea: ☐ Currently being treated ☐ History / No current treatment
- ☐ Allergic rhinitis: _____
- ☐ Previous allergy testing (blood test or skin prick): ☐ Yes ☐ No
- ☐ Immunotherapy shots for allergies: ☐ Yes ☐ No ☐ Currently
- ☐ Non-allergic rhinitis ☐ Yes ☐ No
- ☐ Asthma ☐ Yes ☐ No
- ☐ Chronic rhinosinusitis ☐ Yes ☐ No
- ☐ Nasal polyps ☐ Yes ☐ No
- ☐ Viral upper respiratory infection ☐ Yes ☐ No
- ☐ Prior ear/sinus surgery ☐ Yes ☐ No
- ☐ Migraine headache history: ☐ Resolved/past diagnosis ☐ Present/medicated ☐ Present/not medicated

- _____
- ☐ Height (ft/in): _____
- ☐ Weight (lbs): _____

Rhinoscopy:

Septal Deviation: None Mild Moderate Severe Nasal

valve collapse: None Mild Moderate Severe Bleeding:

None Yes

Crusting: None Yes

Otoscopy: Normal Abnormal findings: _____

Baseline exhaled NO measurements

Resting peak: _____

10 second peak: _____

3 minute peak: _____

AIM 1: DAY 1 REPEAT EXAMINATION

Rhinoscopy:

Septal Deviation: None Mild Moderate Severe Nasal
valve collapse: None Mild Moderate Severe Bleeding:

Crusting: None Yes
None Yes

Otoscopy: Normal Abnormal findings: _____

Day 1 exhaled NO measurements

Resting peak: _____

10 second peak: _____

3 minute peak: _____

Day 1 patient satisfaction/safety

How much pain did you experience using device? None Mild Moderate Severe

Would you use device again? Yes No

Would you recommend device to others? Yes No

AIM 2, ETD: Patient Medical History and exam

SinuSonic Study

PI: [name]

Subject ID#: _____ Subjects Initials: _____

DEMOGRAPHIC AND CLINICAL VARIABLES (If not previously collected):

Age at enrollment (years):

--	--

Gender: Male Female

What is/was your profession (current/retired)? _____

LANGUAGE, ETHNICITY, RACE, MARITAL STATUS

Please mark one of the following categories which describes your native language:

- ☐ American English
- ☐ Other: please specify _____

Please mark one of the following categories which describes your ethnicity:

- ☐ Not Hispanic or Latino
- ☐ Hispanic or Latino

Please mark one or more of the following categories which describes your race:

- ☐ American Indian or Alaska Native
- ☐ Asian
- ☐ Black or African American
- ☐ Native Hawaiian or Other Pacific Islander
- ☐ White
- ☐ Other

SMOKING HISTORY1. Do you **currently** smoke tobacco products? Yes No (If No please go to question 2)

How many tobacco products do you use in a day? _____ Singles Packs

CURRENT MEDICATION USAGE

- | | | |
|---|------------------------------|-----------------------------|
|  Nasal steroid sprays (Flonase, Nasonex, etc) |  Yes |  No |
|  Nasal antihistamine spray (Astelin, etc) |  Yes |  No |
|  Oral antihistamines (Allegra, Claritin, Benedryl, etc) |  Yes |  No |
|  Oral decongestant (Sudafed, etc) |  Yes |  No |
|  Mucolytic (Mucinex, etc) |  Yes |  No |
|  Luekotriene (Singulair, etc) |  Yes |  No |

COMORBID MEDICAL CONDITIONS: Check box and provide details if present

- ☐ Depression history: ☐ Resolved/past diagnosis ☐ Present/medicated ☐ Present/not medicated
☐ Anxiety history: ☐ Resolved/past diagnosis ☐ Present/medicated ☐ Present/not medicated
☐ Obstructive Sleep Apnea: ☐ Currently being treated ☐ History / No current treatment
☐ Allergic rhinitis: _____
☐ Previous allergy testing (blood test or skin prick): ☐ Yes ☐ No
☐ Immunotherapy shots for allergies: ☐ Yes ☐ No ☐ Currently
☐ Non-allergic rhinitis ☐ Yes ☐ No
☐ Asthma ☐ Yes ☐ No
☐ Chronic rhinosinusitis ☐ Yes ☐ No
☐ Nasal polyps ☐ Yes ☐ No
☐ Viral respiratory infection ☐ Yes ☐ No
☐ Prior ear/sinus surgery ☐ Yes ☐ No
☐ Migraine headache history: ☐ Resolved/past diagnosis ☐ Present/medicated ☐ Present/not medicated

- _____
☐ Height (ft/in): _____
☐ Weight (lbs): _____

Rhinoscopy:

Septal Deviation: None Mild Moderate Severe Nasal
valve collapse: None Mild Moderate Severe Bleeding:

Crusting: None Yes
 None Yes

Otoscopy: ☐Normal ☐Retracted no effusion ☐Effusion

Valsalva: ☐Successful ☐Not successful

Tympanogram type: A B C

AIM 2, ETD: Baseline Questionnaires

PATIENT QUESTIONS	
How long have you had eustachian tube problems? <3 months 3-6 months 6-12 months 1-3 year >3 years	
OVER THE LAST FEW MINUTES, HOW TROUBLESOME HAVE THE FOLLOWING SYMPTOMS BEEN? PLEASE PLACE A MARK ON THE LINE.	
	Not troublesome Worst thinkable/troublesome
Ear pressure	◆—————◆
Feeling that ears are clogged	◆—————◆
Cracking/popping of ears	◆—————◆
Muffled hearing	◆—————◆
Tinnitus (noise in ears)	◆—————◆
OVERALL ASSESSMENT OF EAR and EUSTACHIAN TUBE PROBLEMS	◆—————◆

BASELINE ETDQ-7

Next to each question, circle the number that best describes how you feel.

During the past 1 month, how much of a problem was each of the following?	No problem		Moderate Problem			Severe Problem	
Pressure in the ears?	1	2	3	4	5	6	7
Pain in the ears?	1	2	3	4	5	6	7
A feeling that your ears are clogged or "under water"?	1	2	3	4	5	6	7
Ear problems when you have a cold or sinusitis?	1	2	3	4	5	6	7
Crackling or popping sounds in the ears?	1	2	3	4	5	6	7
Ringing in the ears?	1	2	3	4	5	6	7
A feeling that your hearing is muffled?	1	2	3	4	5	6	7

Do you get these symptoms in one ear only or both ears?

Left ear only

Right ear only

Both ears

INCLUSION CRITERIA (all must be yes):

Does patient have ETD sx for ≥ 6 mos? Yes No

Is ETDQ-7 score ≥ 3 ? Yes No

Does patient have ≥ 3 ETD symptoms above? Yes No

AIM 2, ETD: Follow Up Questionnaire 5 minutes**FOLLOW UP ETD VAS 5 MINUTES**

OVER THE LAST FEW MINUTES, HOW TROUBLESOME HAVE THE FOLLOWING SYMPTOMS BEEN? PLEASE PLACE A MARK ON THE LINE.	
	Not troublesome Worst thinkable/troublesome
Ear pressure	◆—————◆
Feeling that ears are clogged	◆—————◆
Cracking/popping of ears	◆—————◆
Muffled hearing	◆—————◆
Tinnitus (noise in ears)	◆—————◆
OVERALL ASSESSMENT OF EAR and EUSTACHIAN TUBE PROBLEMS	◆—————◆

AIM 2, ETD: 6-Week Follow Up Questionnaires

Objective Evaluation			
Rhinoscopy:			
Bleeding:	None	Yes	
Crusting:	None	Yes	
Otoscopy:	 Normal	 Retracted no effusion	 Effusion
Valsalva:	 Successful	 Not successful	
Tympanogram type:	A	B	C

OVER THE LAST FEW MINUTES, HOW TROUBLESOME HAVE THE FOLLOWING SYMPTOMS BEEN? PLEASE PLACE A MARK ON THE LINE.		
	Not troublesome	Worst thinkable/troublesome
Ear pressure		
Feeling that ears are clogged		
Cracking/popping of ears		
Muffled hearing		
Tinnitus (noise in ears)		
OVERALL ASSESSMENT OF EAR and EUSTACHIAN TUBE PROBLEMS		

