2.0 Background

Eustachian tube dysfunction (Meyer TA, etal) and sinus pain/pressure impact the quality of life of millions of Americans (Falco JJ, etal). It is thought that these disorders may be due to positive or negative pressure differential between the middle ear or paranasal sinuses. Current treatment options for ETD and sinus pressure/pain are typically Valsalva (positive expiratory pressure) with the hopes of equalizing pressures between the middle ear space or paranasal sinuses and the nasal cavity/external environment. Pharmacologically, nasal steroid sprays can be used to try to open the ET and sinus drainage pathways. If this fails, then procedures to include pressure equalization tubes (PETs) or balloon eustachian tube/paranasal sinus dilation are offered.

Future treatment options: This study aims to test the safety, efficacy and potential mechanism of action of the SinuSonic device on adults with ETD or facial pain/pressure. SinuSonic is a medical device that utilizes sound and pressure combined with normal breathing. It has been shown to be safe and relieve nasal congestion (Soler ZM, etal). The study will have 3 aims. Aim 1 will examine healthy controls with no signs of upper respiratory infection, inflammation, or ETD to determine if exhaled nasal NO is increased. Acoustic energy (humming) has been shown to increase nasal NO dramatically, thus equalization of gas pressures between the middle ear, the paranasal sinuses and the nasal cavity may very well explain any efficacy noted. Aim 2 will be performed to examine therapeutic efficacy for ETD. Aim 3 will be performed to examine therapeutic efficacy for sinus pain/pressure.

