5.0 Number of Subjects

Aim 1, exhaled NO: We anticipate 10 healthy control subjects for the exhaled NO portion of the study.

Aim 2, ETD: This is a pilot study. The anticipated ETD study population is 30 subjects.

Aim 3, Facial pain/pressure: This is a pilot study. The anticipated facial pain/pressure study population is 30 subjects.

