10.0 Data Management

All analyses and graphs will be performed with SPSS 24.0, Sample Power 3.0, and Sigma Plot 10.0 (SPSS, Chicago, IL.). Disease information and demographic variables, such as age, gender, race, quality of life (QOL) scores, and VAS scores will be summarized using frequencies, means, and standard deviation as appropriate. Aim 1 nasal NO metrics will be compared between baseline vs 10 seconds and baseline vs 3 minutes. Aim 2 metrics (ETDQ-7, ETD VAS and tympanogram) will be compared between baseline and 6 weeks. Aim 3 metrics (VAS, BPI-SF, MCQ-SF) will be compared between baseline vs 2 weeks and baseline vs 4 weeks. Categorical variables will be compared using Chi Square or McNemar's test. Continuous variables will be compared using One-Way ANOVA with repeated measures follow by post-hoc analysis. Data regarding safety and patient satisfaction will be summarized for each time point. A p-value ≤ 0.05 will be considered statistically significant. Due to the exploratory nature of this study, no p-value correction (ie Bonferroni) will be applied.

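### The Aim 2 forms record the tympanogram only as type A, B or C, so the one listed comparison that is not self-reported cannot quantify a pressure change and misses any shift within a type

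*Combined protocol and SAP*

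**What the plan says.** The Aim 2 baseline form in the appendix (Patient Medical History and exam) has the field "Tympanogram type: A B C". The 6-week form has the same three-letter "Tympanogram type" field. Neither has a field for a numeric reading or for the ear tested. Section 3.0 and the schedule in Section 9.1 say that a tympanogram is done, but not which readings are kept.

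Section 10.0 states: "Aim 2 metrics (ETDQ-7, ETD VAS and tympanogram) will be compared between baseline and 6 weeks". For tests it gives "Categorical variables will be compared using Chi Square or McNemar's test" and "Continuous variables will be compared using One-Way ANOVA with repeated measures follow by post-hoc analysis", with "A p-value ≤ 0.05 will be considered statistically significant". Section 5.0 states: "The anticipated ETD study population is 30 subjects".

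The rationale in Section 2.0 is that "these disorders may be due to positive or negative pressure differential between the middle ear or paranasal sinuses". It offers equalization of gas pressures as a possible explanation of any benefit. The Aim 2 inclusion criteria in Section 4.0 require a diagnosis, symptoms and an ETDQ-7 score, but no abnormal tympanogram.

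**The concern.** Aim 2 is a single group using a device they know they are using, and two of its three listed metrics are self-ratings. The tympanogram is the listed comparison least exposed to that problem, and it is also the one closest to the pressure rationale. Reducing it to three letters costs information in three ways:

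- The size of a pressure change cannot be estimated from the forms.
- A subject whose pressure moves without crossing a type boundary counts as unchanged.
- A subject already in the best category cannot improve.

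With 30 subjects, a null result on type would therefore say little about whether pressure moved.

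**Working it through.** **Plan's own figure.** N = 30 is stated without an effect size, SD or power, so there is nothing to reproduce.

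**Step 1: what type alone requires.** Inputs from the documents are n = 30, alpha 0.05 and McNemar's test. Assumptions: two-sided testing (sidedness is not stated), type A as normal (the types are not defined), and types collapsed to A against not A, because simple McNemar needs two categories. If k subjects change and all go one way, the exact p-value is 2 × 0.5^k.

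- k = 5: 2 × 0.03125 = 0.0625, not significant.
- k = 6: 2 × 0.015625 = 0.031, significant.
- One change in the wrong direction raises the minimum to 9 changes, 8 against 1: 2 × (9 + 1)/512 = 0.039.

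The minimum is thus 6 of 30, or 20% of the sample. If 20–60% are not type A at baseline (assumed), only 0.20 × 30 = 6 to 0.60 × 30 = 18 subjects can improve. At the lower end all 6 must improve and nobody may worsen.

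Exact McNemar power at n = 30, averaged over the number who change:

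| Improve | Worsen | Power |
|---|---|---|
| 20% | 3–5% | 24–34% |
| 40% | 3–5% | 82–91% |

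**Step 2: illustrative comparison, uniform shift.** None of these inputs is in the documents: bivariate normal peak pressure, SD 80 daPa, pre-post correlation r, boundary at −100 daPa, baseline mean −60 to −150 daPa, one ear per subject, no flat traces. Each setting used 20,000 simulated trials, with a paired t-test on pressure and exact McNemar on type.

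The SD of the change is 80 × √(2(1 − r)). At r = 0.7 it is 80 × √0.6 = 62.0 daPa, so a 30 daPa shift is 30/62.0 = 0.48 SD. At r = 0.5 it is 80 daPa, and the same shift is 0.375 SD. The share below the boundary at baseline is Φ((−100 + 60)/80) = 31% at mean −60 and Φ((−100 + 150)/80) = 73% at mean −150.

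| r | Shift (daPa) | Power, signed pressure change | Power, type |
|---|---|---|---|
| 0.7 | 20 | about 40% | 7–10% |
| 0.7 | 30 | about 73% | 14–21% |
| 0.7 | 40 | 92–93% | 25–38% |
| 0.7 | 60 | over 99% | 52–76% |
| 0.5 | 30 | 51% | 13–18% |

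A signed-rank test in place of the t-test keeps 69–72% at 30 daPa and r = 0.7.

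**Step 3: the same model, but pressure moves toward zero.** Section 2.0 allows the differential to have either sign. Set follow-up pressure to 0.7 × its no-effect value (30% shrinkage), with baseline mean −30 daPa and r = 0.7. Power is about 13% on signed change, 12% on type and 66% on change in distance from zero.

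**Step 4: the reverse check.** Under the uniform 30 daPa shift of Step 2 (r = 0.7), distance from zero has about 22%, 50% and 67% power at baseline means of −60, −100 and −150, below the 73% for signed change. Neither summary is best for both effect shapes.

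**The case against.** Several stronger readings are tempting, and the documents do not support them.

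- **That the metric cannot show an effect.** It can show a large one: 82–91% power if 40% improve and 3–5% worsen.
- **That the pressure reading is discarded.** The forms have no field for it, but nothing says that the tracing is not kept in source records.
- **That Aim 2 is meant to test pressure change.** Section 1.0 assigns mechanism to Aim 1, through nasal NO, and gives Aim 2 safety and efficacy. Pressure is background rationale, not a named endpoint. Without a control arm, a numeric shift would not establish mechanism either.
- **That this is the trial's only objective measure.** Aim 1 measures NO, and otoscopy and Valsalva are recorded at both Aim 2 visits. The statement is true only of the Aim 2 comparison list in Section 10.0.
- **That staff who know the visit assign the letter.** No section says who classifies the trace.

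The size of the loss is also open to challenge. The SD, boundary and baseline mean are assumed, the model leaves out flat traces, and the advantage of signed change disappears if pressures move toward zero from both sides. That objection stands against any single power figure and against a remedy based on signed change alone. It does not touch what can be read from the forms: no numeric field, no credit for within-type shifts, and no room for improvement in subjects who enter at type A. The plan's status as an exploratory pilot lowers the stakes, but a pilot also benefits from an estimate of size and spread, which three letters cannot give.

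**Conclusion.** The point holds in a limited form. The only Aim 2 comparison in Section 10.0 that is not self-reported is held on a three-category scale. It can register a large movement between types, but it cannot measure a pressure change or detect one within a type.

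The firm figure is the minimum of 6 changes among 30 subjects. It needs only n, alpha, a two-sided exact McNemar test and a collapse to two categories. The power comparisons rest wholly on assumed values. They show that the loss may be large (about 73% against 14–21%) for a moderate uniform shift, and that the gain from a numeric reading depends on analysing it in a way that fits the expected effect. The gap does not invalidate the pilot, and it is cheap to close.

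**What to change.** 1. **Forms.** Add a numeric peak-pressure field (daPa, or flat with no peak) for each ear at baseline and week 6, read from the tympanogram already performed.
2. **Section 10.0.** Prespecify the paired change in distance of peak pressure from zero as the tympanogram analysis, since Section 2.0 posits a differential of either sign. Report signed change alongside it, because distance from zero is the weaker summary if the effect is a uniform shift.
3. **Ear.** State which ear is analysed, for example the worse symptomatic ear at baseline. The form asks only whether one or both ears are affected, so subjects with both need a question on which is worse. Choosing the ear by its baseline pressure would invite regression to the mean in an uncontrolled group.
4. **Flat traces.** Use a paired rank-based or sign test that orders flat as worst. Flat to a measurable peak counts as better, the reverse as worse, and flat at both visits as a tie. A signed-rank test needs a stated score for flat, beyond the largest observed distance.
5. **Type.** Keep A, B and C as a descriptive baseline-by-week-6 table.

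The cost is one reading per ear on each form, one question on the worse ear and a short analysis paragraph. No visit or procedure is added. The downside is that flat traces have no peak value and need the ordering rule; power with that rule was not evaluated here.
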